Reducing numbers of hospital stays and days of stays, numbers of physician and nurse visits with records of symptoms, number of dispensed medicines, medical expenses; in the HbA1c% intervention - reduced number of dispensed anti-diabetes medicines and reduced rate of measuring glucose levels of 70 mg/dL or less ; in the cholesterol intervention - reduced number of dispensed anti-cholesterol medicines.

Increasing rate of weight measuring, BMI level, HbA1c% measuring, HbA1c% level, cholesterol measuring, cholesterol level; in the BMI intervention - percentage of patients evaluated by a nurse and counseled by a dietician.

Methodology:

Briefly: This prospective, randomized controlled trial, will compare BMI, HbA1c% and cholesterol values, rate of death, number of stays, days of stays, numbers of physician and nurse visits with records of symptoms such as "weakness", "dizziness" and total medical expenses of patients 75 years and older that their clinic staff will receive the email concerning them, versus patients that such email concerning them will not be sent. The trial has 3 different alerts: 1. An alert about a significant drop in BMI; 2. An alert about low HbA1c% level in patients treated with diabetes medicines; and 3. An alert about hypocholesterolemia in patients treated with cholesterol-lowering medicines.

Recruiting and inclusion criteria: 75 years and older at the beginning of the trial, clients of Clalit health Services at the North and the South districts, which will be identified thru the computer system (BO) as having one or more of the following:

For alert no. 1: A drop in BMI of 2 Kg/m² or more during the last two years and¹ a BMI lower than 23 Kg/m² and¹ no dietician counseling during the last year.

For alert no. 2: HbA1c% of 6.5% or less and¹ dispensing diabetes medicines during the last 2 months.

For alert no. 3: Total cholesterol less than 160 mg/dL and¹ dispensing cholesterol-lowering medicines during the last 2 months.

Exclusion criteria:

General: Clients that an email address of their physician or nurse is not found.

For alert no. 3: Clients with a diagnosis of myocardial infarction, ischemic heart disease, transient ischemic attack or cortical cerebrovascular accident.

Study schedule:

Sending the alerting mails will be done in one-session during 2015.

Collecting the data will be done after one year.

Publishing the main results will be done within another year at the latest (2017).

Study procedures and methods:

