- a. Randomization aims to get an unbiased and equal division into an intervention group and a control group.
- b. Randomization will be via computer: by adding a column in the excel table, with the function =ROUND(RAND(),0). This means 1:1 randomization to 0 (control) or 1 (intervention letter).
- c. In order to avoid large differences in numbers of participants among the subgroups, the randomization procedure will repeat until the difference between control and intervention group is less than 2%.

3. The alert emails will be prepared and sent via "Mail Merge" (of Microsoft Word) to the primary physicians and to the nurses in charge at the same clinics. The templates to those emails are shown in the appendix. Technical problems (e.g. full mailbox of recipients) will be recorded and managed promptly (- days, hopefully), by the principal investigator.

4. Collecting outcome data: will be via the Clalit health services computer system. Data will include:

a. For all participants (control and trial groups), for the year that follows the intervention email:

1. Mortality (of any cause)
2. Days in stays (of any ward)
3. Number of stays
4. Number of physician visits
5. Number of nurse visits with symptoms
6. Number of all medicines dispensed
7. Medical expenses
8. Last BMI level and date
9. Last cholesterol level and date
10. Last HbA1c% level and date
11. Glucose levels of 70 mg/dL or less, and dates

b. For alert 1., for the year that follows the intervention email:

1. Recording of functional estimation by a nurse
2. Recording nutritional estimation by a nurse
3. Recording dietitian consultation

c. For alert 2. on the 3 months that follows the intervention email:

1. Whether a diabetes medicine was dispensed, and if so:
2. Name of diabetes medicine, dose and quantity

d. For alert 3. on the 3 months that follows the intervention email:

1. Whether a cholesterol lowering medicine was dispensed, and if so:
2. Name of medicine, dose and quantity

5. Data security: will be handled according to Clalit health systems procedures. The information will be saved in allowed secure servers only and will be available to authorized researchers only after their guidance and signing a non-disclosure commitment. When applicable, personal identification details will be omitted from the lists.

6. Outcome analysis:

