This letter is sent to you as a part of an authorized clinical trial. Details about the trial can be found in [this link](#). **Briefly:** Patients aged 75+ with signs of a metabolic risk were found via computer. This detection included **low HbA1c% (<6.5%) with anti-diabetic medicines**, etc. After randomization to control and intervention groups, relevant alerts are sent for the intervention groups. In this trial we will check the effect of these alerts on treatment, health indexes and survival – a year from now.

Mrs./Mr. _____ , I.D. _____, at _____ clinic of yours, was lately found to take anti-diabetic medicine (_____) and the HbA1c% was _____. This level is low for diabetic medical treatment. According to current guidelines and quality-indicators, a level somewhat below 8% is satisfying and safer.

We ask you to consider **re-estimation** of his functional and medical condition and of his treatment, including **lowering the dose of the anti-diabetic medicine**.

We will be grateful for cooperation and will be happy to discuss any questions,

Sincerely,

[name] (Principal investigator)

[name]

[contact]

[contact]

Further background:

Correlation between death and HbA1c% is U-shaped, with increased mortality under the level of 6.5% in patients taking two antidiabetic medicines (Currie, 2010). Among these patients, the optimal HbA1c% values of for survival were 7.5-8%. Updated quality-measures consider <8% is satisfying for diabetic patients of age 75+ years.

Appendix 3. Template for email regarding a patient with low cholesterol that took a cholesterol lowering medicine.

Email Subject:

LIMIT-C trial alert: Low cholesterol level of your patient – Mrs./Mr. _____ , I.D.

Email Body:

Dear Dr./Mrs./Mr. _____ ,

This letter is sent to you as a part of an authorized clinical trial. Details about the trial can be found in [this link](#). **Briefly:** Patients aged 75+ with signs of a metabolic risk were found via computer. This detection included **low cholesterol (<160mg%) with cholesterol lowering medicines**, etc. After randomization to control and intervention groups, relevant alerts are sent for the intervention groups. In this trial we will check the effect of these alerts on treatment, health indexes and survival – a year from now.

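### The hypothesis concerns physician visits with recorded symptoms, but the data list collects all physician visits, so that half of the hypothesis goes untested and visits prompted by the letter could mask or reverse a benefit

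*Combined protocol and SAP*

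**What the plan says.** In the detailed list under Study Hypotheses, B, the quantities expected to fall include "numbers of physician and nurse visits with records of symptoms". The short summary that opens Methodology names the same outcome again and gives weakness and dizziness as examples. The protocol contains no fuller list of symptoms.

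Under Study procedures and methods, 4. Collecting outcome data, item a.4 is "Number of physician visits" and item a.5 is "Number of nurse visits with symptoms". Both cover the year after the email.

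The letters in Appendices 1 to 3 all ask the recipient to consider a re-estimation "of his functional and medical condition and of his treatment". Section 6, Outcome analysis, compares the arms on continuous variables by t-test or Wilcoxon test at P < .05. It has no rule for separating visits prompted by the letter from visits brought on by symptoms.

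**The concern.** Two things follow from the missing condition in a.4. First, the variable collected is not the variable hypothesised. Second, the substitute is one that the intervention may itself raise. A clinician who acts on the letter may call the patient in, and that visit enters a count which the protocol hopes to see fall. The protocol expects more contact in other respects: the same list of hypotheses foresees more weight, HbA1c and cholesterol measurement and, for the BMI alert, more nurse evaluation and dietician counselling.

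At stake is one secondary outcome. The main hypotheses, on mortality and on change in the three indices, do not depend on it.

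**Working it through.** **Step 1: the texts side by side.**

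| Place | Physician visits | Nurse visits |
|---|---|---|
| Study Hypotheses, B | with recorded symptoms | with recorded symptoms |
| Methodology summary | with recorded symptoms (two examples) | with recorded symptoms (two examples) |
| Data items a.4 and a.5 | all visits | with symptoms |

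The remaining items under 4a to 4d cover death, hospital stays, medicines, expenses, laboratory and BMI values, and nurse or dietician assessments. None records symptoms at a physician visit.

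**Step 2: inputs for the size.** The plan gives no figure for visits that could be reproduced. Its only power statement concerns mortality (3% against 1.8%). From the plan: about 10,000 patients allocated 1:1, so n = 5,000 per arm, and a significance level of 0.05. Assumed: a two-sided test, independent patients, and an SD of 8 to 12 physician visits per year. The numbers of prompted and avoided visits below are also assumptions.

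**Step 3: effect of net extra visits.** z = d / (SD × √(2/n)), where d is the net difference in visits per patient. With n = 5,000, √(2/n) = 0.02, so the standard error is 8 × 0.02 = 0.16 or 12 × 0.02 = 0.24.

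| d | z, SD 8 | z, SD 12 |
|---|---|---|
| 0.2 | 0.2/0.16 = 1.25 | 0.2/0.24 = 0.83 |
| 0.5 | 0.5/0.16 = 3.12 | 0.5/0.24 = 2.08 |

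The difference that just reaches P < .05 is 1.96 × 0.16 = 0.31 or 1.96 × 0.24 = 0.47 visits per patient.

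**Step 4: a single alert group.** If the three alerts made up equal thirds (an assumption), n would be about 1,667 per arm and √(2/1,667) = 0.0346. Then d = 0.5 gives z = 0.5/0.277 = 1.80 (SD 8) or 0.5/0.416 = 1.20 (SD 12).

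**Step 5: prompted visits set against avoided visits.** Net difference = prompted visits per patient − (symptom visits per year × relative reduction).

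- 0.5 − 1 × 0.10 = +0.4: the sign is wrong (z = 2.5 for SD 8, 1.67 for SD 12).
- 0.3 − 3 × 0.10 = 0: a real reduction is hidden.
- 0.1 − 5 × 0.20 = −0.9: the sign is right (z = −5.62 for SD 8, −3.75 for SD 12).

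The same mechanism can therefore reverse a benefit, hide it or leave it visible, depending on rates that the documents do not give.

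**The case against.** The strongest defence is that a.4 is a terse entry in a document translated from Hebrew, and the condition may simply have been lost. That is possible, but the next line keeps it, and whoever writes the query will work from the list.

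A second defence reads the symptom condition in the hypothesis as applying to nurse visits only, so that a.4 and a.5 match it. This is the less natural reading. It also leaves the hypothesis as fewer physician visits of any kind after a letter that invites reassessment, so the problem of prompted visits stays.

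A third defence stands in part. The letters ask clinicians only to consider reassessment, and none requests a visit. Record review, a treatment change without a visit, or a visit already planned would all comply, so extra visits are an inference.

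A reader might infer that a letter that works would be scored as worse. The documents do not support this: it requires prompted visits to outnumber avoided ones, and no rates are given.

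A reader might also extend the point to low glucose, where the hypothesis is a "reduced rate of measuring glucose levels of 70 mg/dL or less" and item a.11 collects "Glucose levels of 70 mg/dL or less, and dates" without a count of tests. That does not hold as a parallel fault. Events per patient over the stated year, or the share of patients with a low value, can be calculated from a.11. The letter in Appendix 2 does not ask for glucose testing, and the hypothesised increases in measurement do not include glucose.

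**Conclusion.** The mismatch is on the face of the protocol and needs no assumption: as listed, the data cannot test the physician half of the visit hypothesis. That the all-visit count is open to bias against the letter is a reasonable inference from the letters' request and the one-year window. How large the bias is, and whether it changes the sign, cannot be established. The illustrative range runs from a negligible effect at 0.2 net extra visits to nominally significant apparent harm at 0.5, pooled over both districts, and it rests wholly on assumed SDs and visit numbers. The point should be corrected, but it touches one secondary outcome only.

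**What to change.** Reword item a.4 so that it counts physician visits with a recorded symptom. Fix one list of symptom codes or terms before the data pull and apply it to both a.4 and a.5. The list has to be written, because a.5 has none to copy. Compare the arms on the count per randomised patient over the year. Report total physician visits separately as a process measure with no hypothesised reduction.

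Do not use symptom visits per total visit, or low glucose values per test, as outcomes. The letter can change those denominators after randomisation, and extra routine visits or tests would dilute the ratio in the letter's favour. A total glucose-test count may be reported as a descriptive process measure only.

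The cost is one changed field, one retained field and a short symptom list, in an extraction that is already planned. The change does not remove all bias. Symptom recording at physician visits may be incomplete, and a letter may itself prompt more of it; Appendix 3, for example, names adverse effects to consider. A sensitivity analysis that leaves out a pre-specified early window after the email, dated identically for control patients, would help. It needs visit dates, which a.4 and a.5 do not currently request.

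### Diabetes and cholesterol-lowering medicine dispensing is collected only for the 3 months from the email, with no lag: the yes/no item can mask full stops, and class-specific changes after month 3 are not collected

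*Combined protocol and SAP*

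**What the plan says.** All references are to Study procedures and methods, 4. Collecting outcome data, unless stated otherwise.

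- Item c is collected "For alert 2. on the 3 months that follows the intervention email". Its contents are "Whether a diabetes medicine was dispensed, and if so", followed by "Name of diabetes medicine, dose and quantity".
- Item d is collected "For alert 3. on the 3 months that follows the intervention email", with the matching yes/no question and "Name of medicine, dose and quantity".
- Item a is collected "For all participants (control and trial groups), for the year that follows the intervention email". It covers mortality, hospital stays, visits, expenses, "Number of all medicines dispensed", the last BMI, cholesterol and HbA1c with dates, and low glucose values. The alert 1 process measures in item b also run for the year.
- Study schedule: "Collecting the data will be done after one year".
- Study Hypotheses: fewer dispensed anti-diabetes and anti-cholesterol medicines are listed among the other (not main) hypotheses, with no time limit.
- Recruiting and inclusion criteria: eligibility for alerts 2 and 3 requires a dispensing of the medicine class in the preceding 2 months.
- Appendices 2 and 3: the emails ask the clinician to consider reassessment, including a lower dose. They say that the effect on treatment, among other things, will be checked a year later.

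The plan does not say whether name, dose and quantity are taken from every dispensing, from the last one or as a total, nor whether dispensing dates are kept. It gives no supply length and no expected time from email to clinician action.

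**The concern.** Dispensing is the direct measure of whether the letters for alerts 2 and 3 changed drug treatment. Two features of its window weaken it.

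First, the window starts at the email, before anyone has read it or seen the patient. Every eligible patient has recently been dispensed the medicine, so some will refill under the existing prescription before a decision is made. A stop that follows such a refill looks, on the yes/no item, the same as no change.

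Second, the window closes at month 3. A change made later, or a restart, leaves no class-specific record, although death is counted over twelve months. If mortality does not differ, the investigators will want to know whether treatment changed and stayed changed. The dispensing data will speak only to the first quarter of the year.

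**Working it through.** The plan gives no figure for this outcome, so there is nothing to reproduce. The size of the masking has to be bounded by assumption.

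**Input from the plan.** Window length: 3 months, taken as 90 days from the email.

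**Assumed inputs.** Refill interval R = 30 or 90 days. First refill after the email at time U, uniform on 0 to R. Clinician action at time T, uniform on 0 to A, with A = 60, 90 or 180 days.

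**1. Full stop, yes/no item.** The stop is visible only if it precedes the first refill, so P(visible) = P(T < U) = E[min(U, A)]/A.

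- R = 30: E[U] = 15, giving 15/60 = 25%, 15/90 = 17% and 15/180 = 8%.
- R = 90: for A = 60, E[min(U, 60)] = (60²/2 + 30 × 60)/90 = 40, giving 40/60 = 67%. For A = 90 and 180, E[U] = 45, giving 45/90 = 50% and 45/180 = 25%.

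The range is 8% to 67%. A true 20-point difference in stopping would appear as 20 × 0.083 = 1.7 points at one end and 20 × 0.667 = 13.3 points at the other.

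**2. Fixed delay.** If action comes at day d and supply lasts S days, the share of stops masked is min(1, d/S). More than half are masked only when d exceeds 15, 30 or 45 days for S = 30, 60 or 90.

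**3. Dose reduction, if the last record in the window is kept.**

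- R = 30: the last refill in the window is at U + 60, so P(visible) = P(T < U + 60). This is 100% for A = 60, 75/90 = 83% for A = 90 and 75/180 = 42% for A = 180.
- R = 90: there is one refill in the window, so the results equal those for a full stop: 67%, 50% and 25%.

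**4. Total quantity.** For a permanent stop, the share of its effect kept is the average fraction of the window that lies after T.

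| A (days) | 90-day window | 365-day window |
|---|---|---|
| 60 | 1 − 30/90 = 67% | 1 − 30/365 = 92% |
| 90 | 1 − 45/90 = 50% | 1 − 45/365 = 88% |
| 180 | 22.5/90 = 25% | 1 − 90/365 = 75% |

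In the last row, 22.5 is the mean number of days left in the 90-day window: (90²/2)/180.

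**5. What a longer window alone does.** It recovers most of the quantity measure. It does not repair the yes/no item, because one refill before the stop still counts as dispensed however long the window is. That item needs a later start, or dated records.

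**The case against.** A reader might infer that the window hides most treatment changes. The documents do not support that. The refill interval and the delay are not stated, and the 2-month look-back for eligibility does not establish monthly refills. At 90-day refills, half or more of full stops stay visible when action falls within 90 days. The emails ask for a lower dose, not only for stopping, and items c and d collect dose and quantity. With 30-day refills and action over 90 days, 83% of dose reductions would show in the last record, against 17% of full stops on the yes/no item. The baseline table (1. Finding the participants) takes name, dose and quantity from the last medicine dispensed, so a before-and-after comparison is possible if the outcome is read in the same way. This part of the objection stands, subject to the plan saying which record is used.

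A reader might also infer that a null mortality result could not be interpreted at all. That goes too far. The main compliance hypothesis concerns the index itself, and the last HbA1c and cholesterol are collected over the full year in both arms. They respond to sustained changes and restarts. They are still indirect: they exist only for patients who are retested, and the plan expects the letter to raise testing rates, so the retested groups may differ between arms. The yearly count of all medicines carries neither class nor dose.

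Finally, a 3-month measure is a defensible early process outcome, and the error from early refills cannot create a difference in favour of the letter. Both points are right. They argue for keeping months 0-3, not for stopping there.

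**Conclusion.** The concern holds in a limited form. The yes/no item can mask full stops that follow an early refill: 8% to 67% remain visible under refills every 30 to 90 days and action spread over 60 to 180 days. These inputs are assumptions, and the range is too wide to say that most stops are lost. Dose reductions within the window are captured equally well or better, on condition that each dispensing or the last one is recorded. Class-specific changes and restarts after month 3 are not collected, and this needs no assumption.

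The consequence is dilution toward no difference in a secondary outcome, together with a gap in the evidence on whether treatment change lasted. Mortality and the index outcomes are not affected. The change is worth making because it costs very little and allows the dispensing hypotheses to be tested over the same year as the other outcomes.

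**What to change.** In items 4.c and 4.d:

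1. Extract every dispensing record of diabetes and cholesterol-lowering medicines, with date, name, dose and quantity, for the full year after the mailing date, in both arms. The mails go out in one session, so one date can anchor both arms.
2. Compare the total dispensed quantity or dose over the year, in a unit named in advance that allows different medicines to be combined.
3. Compare dispensing in a later window, for example the last 3 months of follow-up.
4. Keep months 0-3 as an early-response measure, and state which record supplies the dose.

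The cost is a few lines of wording and a longer date range in an extraction already planned at one year from the same system. The one real complication is death before the later window. Comparing survivors only would condition on the trial's main health outcome. A stated rule avoids this, for example analysing all randomised patients by dispensing per day alive, with deaths reported alongside.

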BMI is a widely used as an index of nutritional problems. In a meta-analysis which included 2.88 million people, the optimal BMI for overall survival was found to be 25-30 kg/m² (Flegal, 2013; Dixon, 2014 ; Pan, 2012). Rapid weight loss is a strong indicator for health and functional decline. Such a weight loss, especially with low BMI values, usually mandates investigation in order to eliminate the cause or to limit its effect. A use of an automatic e-mail alert system was found to improve screening rate of malnourished patients in hospital (Giovannelli, 2014).

Correlation between death and HbA1c% is U-shaped, with increased mortality under a 6.5% level in patients taking two antidiabetic medicines (Currie, 2010). Among these patients, the optimal HbA1c% values of for survival were 7.5-8%. A substantial proportion of older adults with diabetes were found by Lipska et al. (2015) to be potentially overtreated.

Correlation between death and cholesterol is also U-shaped (Iso, 1989). Hypocholesterolemia is defined as cholesterol below 160 mg% and predicts increased mortality and morbidity (Hazzard's, p. 1341). We found no interventional study for this situation in the scientific literature.

In our experience, Email alerts to doctors, regarding an over-tight control of specified diabetic patients by sulphonyl-urea medicines was followed by a reduction (from 3% to 1.8%) in

mortality comparing to a previous-year matched control group (unpublished observations). While this result was not statistically significant, it encouraged us to try this large scale interventional clinical trial. It also served us in assessing the size of the study population needed.

Objectives:

This study aims to determine whether reminding physicians and nurses about too low values of weight (as BMI), glucose (as HbA1c%) or cholesterol (as total serum cholesterol) improves survival and health of people older than 75 years.

Study Hypotheses:

A. Main Study Hypotheses:

1. Compliance: Sending the intervention letter will cause a positive change in the relevant index (a rise in BMI, HbA1c%, or cholesterol, respectively).
2. Health effect: Sending the intervention letter will cause a lower mortality rate in each study group compared to control groups, within a year.

B. Other Study Hypotheses: compared to control groups, sending the intervention letter will cause improvement in morbidity and in secondary measures (see below).

And in detail:

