Categorical variables will be shown as frequencies and percentages. Continuous variables will be shown using standard distribution indices (e.g. average, standard deviation, median, etc.). Differences between the arms of the study will be examined using Chi-square test (or Fishers' exact test) for categorical variables and T-test (or Wilcoxon two sample test) for continuous variables. The statistical processing will be performed using Excel or SAS 9.2 software and will be statistically significant if $P < .05$.

7. Ethical issues of the trial:

A waiver of the requirement to obtain a signed informed consent from participants is requested with the following reason: There is no contact with the patients, only unsheathing their existing data.

A waiver of Form 11 is requested with the following reason:

The family physician will be the one who would get the alert related to this trial in the first place.

Appendixes:

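### Low-severity free improvement: the outcome analysis tests the index outcomes without baseline adjustment, although each index has a pre-randomisation value held or needed, and leaves open whether final value or change is tested

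*Combined protocol and SAP*

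**What the plan says.** Hypothesis A.1 (Compliance) is one of the two main hypotheses: "Sending the intervention letter will cause a positive change in the relevant index", meaning BMI, HbA1c or cholesterol for the respective alert. Item 6, Outcome analysis, is the whole statistical plan. For these outcomes it offers a "T-test (or Wilcoxon two sample test) for continuous variables" and names no covariate or model.

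The pre-randomisation values are as follows.

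- **BMI and total cholesterol:** both are fields in the table described in item 1.A.
- **HbA1c:** it is not in that field list. Alert 2 eligibility requires "HbA1c% of 6.5% or less", and the Appendix 2 e-mail prints the patient's value, so it must be retrieved. The list is incomplete, but the value is available.

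The variable to be tested is described in different ways. Hypothesis A.1 speaks of change. The Methodology summary says the trial "will compare BMI, HbA1c% and cholesterol values". The detailed secondary hypotheses list "Increasing rate of weight measuring, BMI level, HbA1c% measuring, HbA1c% level, cholesterol measuring, cholesterol level". Item 4.a collects the last level of each index in the year after the e-mail. Item 6 does not say which variable is tested, or what decides between the two tests.

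**The concern.** A patient's index value at follow-up is likely to be related to the value before the letter. An unadjusted comparison leaves that predictable part in the error term. Adjusting for it needs no new data. It matters most here because each index is tested within its own alert rather than in all 10,000 or so patients, and only patients re-measured after the e-mail contribute. The only sizing calculation is for mortality.

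The open choice between final value and change, and between t-test and Wilcoxon, also allows several p-values for one main hypothesis. Naming one variable and one model in advance removes that choice.

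**Working it through.** **The plan's own figure.** Item 1.C calls about 10,000 patients sufficient, using a chi-square test of 3% against 1.8% mortality. It gives no numeric power. With 5,000 per arm and two-sided 0.05, power is 97.5%, so the statement is credible for pooled mortality. It gives no SD, target difference or correlation for any index, so there is no figure to reproduce for hypothesis A.1.

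**Formulas.** Let ρ be the baseline to follow-up correlation before the eligibility cut-offs (assumed), with equal SDs scaled to 1 and normal data. Let v be the baseline variance left after keeping only low values. Per-patient variances among eligible patients are:

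- linear model with baseline: 1 − ρ²
- final value: (1 − ρ²) + ρ²v
- change score: (1 − ρ²) + (1 − ρ)²v

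The added terms cannot be negative, so the model is at least as precise as a t-test on either variable. The gains in effective sample size are ρ²v/(1 − ρ²) over final values and v(1 − ρ)/(1 + ρ) over change scores.

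**Effect of the cut-offs.** Patients are selected on low values ("a BMI lower than 23", "HbA1c% of 6.5% or less", "Total cholesterol less than 160 mg/dL"), which weakens the correlation. If the lowest 10% qualify, v = 0.169. If the lowest 50% qualify, v = 0.363. Each range below runs from 10% to 50% eligible.

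| Assumed ρ | Correlation among eligible | Gain over final value | Gain over change score |
|---|---|---|---|
| 0.3 | 0.13-0.19 | 1.7-3.6% | 9.1-19.6% |
| 0.4 | 0.18-0.25 | 3.2-6.9% | 7.2-15.6% |
| 0.5 | 0.23-0.33 | 5.6-12.1% | 5.6-12.1% |
| 0.6 | 0.30-0.41 | 9.5-20.4% | 4.2-9.1% |
| 0.7 | 0.37-0.51 | 16.3-34.9% | 3.0-6.4% |

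Example, ρ = 0.7 and 50% eligible: 0.49 × 0.363/0.51 = 34.9% over final values, and 0.363 × 0.3/1.7 = 6.4% over change scores. Below ρ = 0.5 the final value is the better unadjusted choice, and above it the change score is. The adjusted model does not need that to be known.

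**Alert 1's second rule.** Alert 1 also requires "A drop in BMI of 2" kg/m² or more. Simulation under assumed BMI distributions (mean 26, SD 4.5 or mean 28, SD 5; adjacent-year correlation 0.5 or 0.7) gave gains of 7-38% over final values and 3-9% over change scores. The drop rule therefore does not remove the gain.

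**Detectable difference.** At 80% power and two-sided 0.05, this is 2.80 × √(4/n), divided by √(1 + gain). About 10,000 patients each meet at least one of three alerts, so the largest alert has at least 10,000/3 ≈ 3,333, before any physician opt-out. The adjusted column uses the smallest and largest gains over final values (1.7% and 34.9%).

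| Patients in alert | Re-measured (assumed) | Unadjusted final value, SD | Adjusted, SD |
|---|---|---|---|
| 3,333 | 100% | 0.097 | 0.096-0.084 |
| 3,333 | 60% | 0.125 | 0.124-0.108 |
| 1,000 (assumed) | 100% | 0.177 | 0.176-0.153 |

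**Against Wilcoxon.** For a shift in lognormal data with log-SD 0.3-0.4 (assumed; skewness about 0.95-1.3), Wilcoxon is asymptotically 14-32% more efficient than the t-test. Simulated power with 3,333 patients and a 0.09 SD shift was:

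| Correlation among eligible | Log-SD | Wilcoxon | Adjusted model |
|---|---|---|---|
| 0.23 | 0.3 | 79% | 77% |
| 0.23 | 0.4 | 85% | 77% |
| 0.45 | 0.3 | 78% | 82% |
| 0.45 | 0.4 | 85% | 83% |

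**Selective re-measurement.** The detailed secondary hypotheses expect the letter to raise measuring rates. An illustrative simulation had no true effect, with 60% of controls and 70% of the letter arm measured, the latter more often at low baseline. The unadjusted difference was about −0.03 to −0.06 SD and the adjusted one was near 0.

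**The case against.** The strongest case on the other side is that this is optional.

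- **The gain is assumed and may be small.** This stands. At ρ = 0.3 it is only 2-4% over final values. A low correlation is plausible, because alerts 2 and 3 set no limit on the age of the qualifying HbA1c or cholesterol value.
- **Hypothesis A.1 says change, so the final-value gain should not be the headline.** This stands in part. The texts point both ways, so both readings are given equal weight here.
- **No conclusion about adequate power changes.** This stands. No target effect is given for any index, so the documents do not show that hypothesis A.1 is underpowered.
- **Wilcoxon is also planned and can do better.** This stands. A reader might infer that adjustment beats whichever planned test is used. The guarantee covers only the t-test. Wilcoxon targets a different quantity and can be more powerful with skewed data.
- **The loss may not be precision alone.** This stands. A reader might infer that adjusted and unadjusted analyses must estimate the same arm difference among measured patients. That fails if the letter changes who is re-measured according to baseline.

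None of this removes the basic point. A baseline is held or must be retrieved, and the plan neither adjusts for it nor names the variable tested.

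**Conclusion.** The point holds as a low-severity, nearly costless improvement. Adjustment for the pre-randomisation value is at least as precise as a t-test on the final value or on the change. The gain is about 2-35% in effective sample size over final values and 3-20% over change scores. These figures rest on randomisation, large samples, near-normal data, equal SDs in the unselected population, an assumed unselected correlation of 0.3-0.7 and 10-50% eligibility. The documents supply neither the correlation nor the eligible share.

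Three stronger readings are not supported. Omitting a covariate does not make the planned tests invalid, because the arms are randomised. Baseline HbA1c is not unavailable, only missing from a list. No gain follows for mortality. Adjustment also does not deal with clustering by physician or clinic.

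**What to change.** In item 6:

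1. Define the index outcome as the last value recorded in the year after the e-mail.
2. For each alert, analyse the patients eligible for it: subgroups A, D, E, G for BMI; B, D, F, G for HbA1c; C, E, F, G for cholesterol. Make the primary analysis a linear model on arm and the pre-randomisation value of that index, plus age, sex and overlap subgroup. For BMI, use the last value of the last year before randomisation.
3. Keep one named unadjusted test on the same variable as a sensitivity analysis: the t-test, or Wilcoxon if skewness is expected.
4. State that the model uses patients with a value recorded after the e-mail. Report by arm how many have none and how many died. Say that adjusted and unadjusted differences may disagree if the letter changes who is measured, and that adjustment corrects only selection running through the baseline value.

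In item 1.A, add the pre-randomisation HbA1c value to the field list.

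Cost: a few lines in item 6 and one field in item 1.A. No extra patients or visits are needed, and no data beyond what eligibility already requires. SAS, already named, fits the model. The one possible loss is power relative to Wilcoxon if the data are clearly skewed.
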